**6.4.6. Fractional Exhaled Nitric Oxide Throughout the Study**

The concentration of nitric oxide in exhaled breath (FeNO) will be measured at screening, run-in, all on-site visits during treatment period (visits 1, 2, 3, 4, 6, 7, 8, 9, and 10), and follow-up visit (visit 11).

The changes from baseline in FeNO **throughout study** will be analyzed using analyzed using MMRM in a manner analogous to the analysis as described in Section 6.3.2. The baseline FeNo will be used in the analysis model. Per the ICE handling strategy, for patients who did not complete the treatment period, observations after the end of the treatment period will be discarded and treated as missing observations.

## **7. MULTIPLE COMPARISONS AND MULTIPLICITY**

As there are only 2 treatment groups and one primary analysis test in this study, no multiplicity correction is necessary. Secondary endpoints will be considered as hypothesis-generating.

## **8. SAFETY ANALYSIS**

### **8.1. General**

The safety analysis set (Section 3.3) will be used for all safety analyses. Summaries will be presented using descriptive statistics by treatment group as actually received unless otherwise stated. All data will be listed using ITT analysis set unless otherwise specified.

### **8.2. Duration of Exposure to Study Drug**

The patients will receive the IMP loading dose on the day of randomization (visit 1) and the subsequent corresponding IMP maintenance dose every 2 weeks (visits 2 to 4 and visits 6 to 9) for a total of 8 doses ( [REDACTED] ).

Duration of the treatment period (days), the number of doses received, and reasons for IMP not administered (adverse event or other) will be summarized using descriptive statistics.

Duration of the treatment period (days) for a patient is defined as the number of days a patient is in the treatment period and calculated as the date of last IMP administration – the date of first IMP administration + 14.

IMP administration, IMP accountability data, and medical device malfunction data will be listed using safety analysis set.

### **8.3. Adverse Events**

Adverse events will be recorded from time informed consent is obtained through the end of study participation.

All adverse events will be coded using MedDRA. Each patient will be counted only once in each preferred term or SOC category for the analyses of safety. Summaries will include treatment-emergent adverse events which are defined as adverse events occurring at or after the first dose of the IMP through the end of the follow-up visit. Listings will include all adverse events recorded.

Summaries will be presented for all adverse events (overall and by severity), adverse events determined by the investigator to be related to test IMP (defined as related or with missing relationship) (overall and by severity), adverse events determined by the investigator to be related to the medical device, or the study inhaler (defined as related or with missing relationship), serious adverse events, and adverse events causing drug withdrawal or discontinuation from the study. Adverse events with the missing flag indicating serious will be excluded from the summary of serious adverse events but included in the summary of non-serious adverse events.

Summaries for clinical asthma exacerbation related adverse events, loss of asthma control related adverse events, injection site reaction adverse events, protocol-defined adverse events of special interest (PDAESI), PDAESI require completion of suspected anaphylaxis will also be presented.

Listings for deaths, serious adverse events, adverse events leading to drug withdrawn or the study discontinuation, clinical asthma exacerbation related adverse events, loss of asthma control

related adverse events, injection site reaction adverse events, PDAESI, and PDAESI require completion of suspected anaphylaxis, adverse event required concomitant or additional treatment will be presented. In addition, listings for MedDRA dictionary terms for adverse event descriptions and adverse event preferred terms by patient number and treatment group will be presented.

Adverse events for patients who did not meet screening criteria will be listed.

In additional, adverse events and serious adverse events occurred during the 10 weeks period after the last dose of IMP will be summarized using descriptive statistics. These adverse events will be presented in a patient listing as well. Injection Site Assessments

Local tolerability assessments will be performed after each administration of IMP (visits 1 to 4 and visits 6 to 9) and include administration site findings and pain. Administration site findings (erythema, ecchymosis, induration, tenderness, warmth, and swelling) will be assessed using the scales provided in Table 2. Pain at the administration site will be reported using standardized 11-point pain intensity numerical response scale (NRS-11) where 0 is “No pain” and 10 is “Worst possible pain”. Patients will be asked to respond to the following question: “How much pain do you feel at the drug injection site?”

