7.1.2. Recording and Reporting of Adverse Events

For recording of adverse events, the study period is defined for each patient as the time period from signature of the ICF through the EOS visit. The period for reporting treatment-emergent adverse events is defined as the period after the first dose of IMP is administered and until the EOS visit.

All adverse events that occur during the defined study period must be recorded both on the source documentation and the CRF, regardless of the severity of the event or judged relationship to the IMP. Serious adverse events (Section 7.1.5) and/or PDAESI requiring reporting to GPSP (Section 7.1.6) must be reported within 24 hours from the investigator's awareness, using the SAE/PDAESI form (Section 7.1.5.3.1). The investigator does not need to actively monitor patients for new adverse events after the study period defined above.

All device-related adverse events, malfunctions etc. will be recorded and evaluated for their impact relative to the safety and efficacy of the IMP.

At each contact with the patient, the investigator or designee must question the patient about adverse events by asking open-ended questions such as “Have you had any unusual symptoms or medical problems since the last visit? If yes, please describe.” A precise diagnosis should be recorded whenever possible. When such a diagnosis is made, all related signs, symptoms, and any test findings will be recorded collectively as a single diagnosis on the CRF and, if it is a serious adverse event, on the serious adverse event form. Reported or observed signs and symptoms that are not manifestations of a known diagnosis should be reported individually.

The clinical course of each adverse event will be monitored at suitable intervals until resolved, stabilized, or returned to baseline; or until the patient is referred for continued care to a health care professional; or until a determination of a cause unrelated to the IMP or study procedure is made.

The onset and end dates, duration (in case of adverse event duration of less than 24 hours), action taken regarding IMP, treatment administered, and outcome for each adverse event must be recorded both on the source documentation and the CRF.

The relationship of each adverse event to the IMP and to the device, as well as the severity and seriousness of each adverse event, as judged by the investigator, must be recorded as described below.

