7.1.5.3. Reporting a Serious Adverse Event

7.1.5.3.1. Investigator Responsibility

To satisfy regulatory requirements, all serious adverse events that occur during the study, regardless of judged relationship to administration of the IMP, must be reported to the sponsor by the investigator. The event must be reported within 24 hours of when the investigator learns about it. This applies also to Protocol Defined Adverse Events of Special Interests (PDAESI) requiring reporting to GPSP (Section 7.1.6). Completing the SAE/PDAESI form and reporting the event must not be delayed, even if not all the information is available. If any of the

information listed below is not immediately available, it should be provided to the sponsor as soon as possible but the initial reporting to the Sponsor must not be delayed.

Serious adverse events occurring to a patient after the end of the study should be reported to the sponsor if the investigator becomes aware of them.

The SAE/PDAESI form should be sent to the Local Safety Officer (LSO) or designee (a CRO in a country without a sponsor LSO) (contact information is in the Clinical Study Personnel Contact Information section); the LSO will forward the report to the sponsor's GPSP.

The following information should be provided on the SAE/PDAESI form:

- study number
- investigator and investigational center identification
- patient number
- onset date and detailed description of adverse event
- investigator's assessment of the relationship of the adverse event to the IMP (no reasonable possibility, reasonable possibility, as described in [Table 6](#))
- age and sex of patient
- date of first dose of IMP
- date and amount of last administered dose of IMP
- action taken
- outcome, if known
- severity
- explanation of assessment of relatedness
- concomitant medication (including study-provided inhalers, doses, routes of administration, dates, and regimens)
- treatment for the event
- pertinent laboratory or other diagnostic test data
- medical history
- results of dechallenge/rechallenge, if known
- for an adverse event resulting in death
 - cause of death (whether or not the death was related to IMP)
 - autopsy findings (if available)

Each report of a serious adverse event will be reviewed and evaluated by both the investigator and the sponsor to assess the nature of the event and the relationship of the event to the IMP.

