9.8. Safety Analysis

Safety analyses will be performed on the safety analysis set (Section 9.2.2).

Safety assessments and time points are provided in Table 2, Table 3, and Table 4.

All adverse events will be coded using the Medical Dictionary for Regulatory Activities (MedDRA). Each patient will be counted only once in each preferred term or system organ class (SOC) category for the analyses of safety.

Summaries will be presented for

- All treatment-emergent adverse events (overall and by severity) (as defined in Section 7.1.2 and Section 7.1.3)
- Adverse events determined by the investigator to be related to test IMP (ie, reasonable possibility; see Section 7.1.4) (defined as related or with missing relationship) (overall and by severity),
- Serious adverse events (Section 7.1.5.1)
- Protocol-defined adverse events of special interest (Section 7.1.6)
- Adverse events causing withdrawal from the study.

Summaries will be presented by treatment group and for all patients. Patient listings of all adverse events (from signature of the ICF), serious adverse events, and adverse events leading to withdrawal will be presented.

Values and change from baseline in laboratory, ECG, and vital signs measurements data (including the incidence of abnormalities) will be summarized descriptively.

Local tolerability: administration site findings (erythema, ecchymosis, induration, tenderness, warmth, and swelling) and administration site pain will be assessed as described in Section 7.6 and summarized descriptively.

The use of concomitant medications will be summarized by therapeutic class using descriptive statistics.

Physical examination data will be listed and may be summarized descriptively.

For continuous variables, descriptive statistics (n, mean, standard deviation, median, minimum, and maximum) will be provided for actual values and changes from baseline to each time point. For categorical variables, patient counts and percentages will be provided. Descriptive summaries of serious adverse events, patient withdrawals due to adverse events, and potentially clinically significant abnormal values (clinical laboratory or vital signs) based on predefined criteria will be provided as well.

If any patient dies during the study, a listing of deaths will be provided and all relevant information will be discussed in the patient narrative included in the CSR.

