### **4.3. Handling Withdrawals and Missing Data**

For all safety variables, only the observed data from the patients will be used in the statistical analyses, ie, there is no plan to estimate missing data, unless otherwise specified.

Dates that have incomplete information (the month and year or just the year is available) will be estimated for the purpose of calculating variables that are dependent on time if necessary. Day will be estimated as the first day (01) of the month (if month and year of partial date are available) or middle (July 1) of the year (if only year is available), unless otherwise noted. The imputations for partial dates are only for calculation purpose. Original date variables will not be modified. Listings will list dates as collected.

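### SAP 8.3 counts adverse events with a missing seriousness flag as non-serious but missing relatedness as related, so any flag still missing at lock can only bias the serious adverse event summary table downward (low severity)

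*SAP*

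**What the plan says.** SAP 8.3 gives an explicit rule for an adverse event whose seriousness was not recorded: "Adverse events with the missing flag indicating serious will be excluded from the summary of serious adverse events". The rest of that sentence says where these events are placed: "but included in the summary of non-serious adverse events".

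The same paragraph sets the opposite default for causality. Events count as "related to test IMP (defined as related or with missing relationship"), and the wording recurs for events "related to the medical device, or the study inhaler (defined as related or with missing relationship"). Protocol 9.8 uses the same definition for relatedness to the test product, "defined as related or with missing relationship", and has no rule for missing seriousness.

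The general position for safety variables, in SAP 4.3, is that "there is no plan to estimate missing data, unless otherwise specified". The seriousness rule is therefore one of the specified exceptions. It assigns a category to a missing value.

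**The concern.** A blank seriousness flag means that the event was never classified. The plan puts it in the less cautious category and gives no reason, although two other missing judgements in the same paragraph go to the more cautious one. A reader of the serious adverse event table would not know that unclassified events had been left out, because the SAP calls for no footnote or separate count.

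The serious event rate is a main safety output of a Phase 2a study of an immunomodulator. The arms are small and few serious events are likely to be tabulated. Protocol 7.1.1 keeps loss of asthma control and clinical exacerbations out of the adverse event record unless they are more severe than the patient's usual disease course. Protocol 7.1.5.1 does the same for asthma hospitalizations in line with the patient's known course. The serious events that remain are therefore of particular interest, and one event can be visible in the table.

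**Working it through.** The plan gives no figure to reproduce. The check compares the rules and then works out the direction and unit size of the error.

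**The rules side by side**

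| Missing item | Default | Place |
|---|---|---|
| Relationship to test product | Related | SAP 8.3, Protocol 9.8 |
| Relationship to device or study inhaler | Related | SAP 8.3 |
| Seriousness | Non-serious | SAP 8.3 only |

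No other section reverses the third row or adds a summary with missing flags counted as serious.

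**Direction of the error**

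Let S be the number of truly serious events and m the share of them with a missing flag at lock. Events with a missing flag never enter the serious summary, so:

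- the table shows S − mS = S(1 − m);
- the error from this rule is −mS, which is zero or negative.

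The documents do not give m. For assumed values:

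| Assumed m | Share of truly serious events shown, 1 − m |
|---|---|
| 0% | 100% |
| 2% | 98% |
| 5% | 95% |
| 10% | 90% |

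Under the opposite default, let f be the number of truly non-serious events with a missing flag. The table would show S + f, and the error would be zero or positive.

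**Size per patient**

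Protocol 3.2 plans 62 randomized patients per arm, or 87 if the interim analysis leads to the full increase.

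- 1/62 = 0.016, or 1.6 percentage points.
- 1/87 = 0.011, or 1.1 percentage points.

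Two qualifications apply. The denominator will be the safety set of SAP 3.3 (treated patients), which may be slightly smaller than the number randomized. And an arm's overall rate moves only if the patient has no other event flagged as serious.

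**How often the rule could act**

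Several provisions make a missing flag at lock unlikely:

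- Protocol 7.1.2 makes seriousness a required record for each event: "as well as the severity and seriousness of each adverse event, as judged by the investigator, must be recorded as described below".
- Protocol 7.1.5.3.1 gives serious events their own route to the sponsor: "The event must be reported within 24 hours of when the investigator learns about it".
- Protocol Appendix H sends missing data back to the site as queries, requires external data to be compared with the clinical database, and has the investigator approve the data.

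As an assumption, 0 to 2 flags might remain missing in the whole trial. These provisions limit how often the rule applies. They do not change the direction in which it errs when it does.

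**The case against.** The strongest reply is that the rule will almost never operate and that nothing is hidden when it does. A truly serious event would need a blank required field, a query left unresolved, and no correction from the separate serious event report. Opportunistic infections, malignancies and severe systemic reactions are reported by the expedited route whatever their seriousness (Protocol 7.1.6) and have their own summary and listing in SAP 8.3. Deaths are listed and narrated. The event also stays in the all-event summary by severity and in the listing of all adverse events. Safety analysis is descriptive, and the futility and sample size decisions in SAP 13 use loss of asthma control only. All of this stands, and it is why the point is low in severity. It also means that a further call to query missing flags would add nothing, since Appendix H already requires it.

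A second reply is that the two defaults need not match. Relatedness is a causal judgement, while seriousness is defined by listed outcomes, and Protocol 7.1.5.1 treats an event that meets none of them as non-serious. No document requires the same default for both, so the asymmetry is not a contradiction, and the SAP overrides no protocol rule because the protocol has none for missing seriousness. But a blank flag does not show that the criteria were checked and none was met, so Protocol 7.1.5.1 does not supply the missing justification.

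A third reply is that counting every blank as serious exchanges one one-sided error for another. That is correct, and it is a reason to offer a separate row as an alternative.

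A reader might infer that the trial will under-ascertain or under-report serious events. The documents do not support that. The collection, expedited reporting and full listing of events do not depend on this rule. Nor do they support a claim that the comparison between arms is biased: nothing suggests that missing flags would differ by arm in a double-blind trial.

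**Conclusion.** The point holds for the serious adverse event summary table and, as its mirror image, for the non-serious summary. If any seriousness flags are still missing at lock, the error in the serious count is zero or downward, and the plan does not disclose it in the table. If none are missing, the error is exactly zero.

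The likely effect is nil to very small. Each affected patient is worth 1.6 percentage points of an arm at 62 patients, or 1.1 at 87, provided that the patient has no other event flagged as serious. The number of missing flags is not in the documents; 0 to 2 is an assumption. The primary efficacy analysis and the interim decisions are untouched. Severity is low. The case for the change rests on the direction of the error, consistency within one paragraph, and its very low cost.

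**What to change.** Replace the sentence in SAP 8.3. The new text should say that missing seriousness flags are reconciled with the 24-hour serious adverse event reports before lock. Any event whose seriousness is still missing is then counted in the serious adverse event summary, with a footnote giving the number, and is not counted as non-serious.

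An acceptable alternative is a separate row in the serious summary for events with seriousness missing. This avoids both one-sided errors and fits SAP 4.1, which allows a missing category to be displayed where appropriate. The SAP should also say whether the separate listing of serious events follows the same rule, which it does not do now.

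The cost is one or two sentences in the SAP and a minor change to the table program. The downside is a possible slight overcount if a non-serious event has an unresolved flag. The footnote discloses it, and the separate row avoids it.

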**Table 2: Administration Site Finding Severity Assessment**

Test	Response
Erythema	- Absent - Erythema surface diameter 5 mm to ≤50 mm (mild) - Erythema surface diameter >50 to ≤100 mm (moderate) - Erythema surface diameter >100 mm (severe)
Ecchymosis	- Absent - Ecchymosis surface diameter 5 mm to ≤50 mm (mild) - Ecchymosis surface diameter >50 to ≤100 mm (moderate) - Ecchymosis surface diameter >100 mm (severe)
Induration	- Absent - Induration surface diameter 5 mm to ≤50 mm (mild) - Induration surface diameter >50 to ≤100 mm (moderate) - Induration surface diameter >100 mm (severe)
Tenderness Warmth Swelling	- None - Mild - Moderate - Severe

The injection site assessments (erythema, ecchymosis, induration, tenderness, warmth, and swelling) at each visit will be summarized using descriptive statistics. For NRS-11 scale, the worst pain score overall and the pain score at each visit will be summarized descriptively. The data will be listed using safety analysis set.

#### 8.4. Hypersensitivity/Anaphylaxis

The event of anaphylaxis is considered as a PDAESI. The information about all suspected anaphylaxis and hypersensitivity events will be recorded on the Suspected Anaphylaxis CRF. PDAESI will be summaries (Section 8.3).

Suspected anaphylaxis data will be listed.

#### 8.5. Deaths

If any patient dies during the study, all relevant information will be discussed in the patient narrative included in the clinical study report.

#### 8.6. Clinical Laboratory Tests

Clinical laboratory tests (serum chemistry, hematology, coagulation, and urinalysis) will be performed at the time points detailed in Table 2 (screening and run-in), Table 3 (treatment period), and Table 4 (follow-up) of the study protocol. Clinical laboratory tests will be performed using the central laboratory.

Laboratory test results will be presented in standard international (SI) units in summaries. Laboratory values and changes from baseline to each visit and Last Assessment will be summarized using descriptive statistics. Shifts (below [low], within [normal], and above [high] the normal range) from baseline to each postbaseline visit and the Last Assessment will be summarized using patient counts. Baseline is defined as the last observed data before the administration of the first dose of the IMP (also see Section 4.2).

The potentially clinically significant abnormal values will be derived using criteria specified in Table 3 based on all postbaseline values (including scheduled, unscheduled, and withdrawal visits). The overall incidence of potentially clinically significant abnormal values will be summarized for laboratory variables using descriptive statistics by treatment group. Listings for patients who have potentially clinically significant abnormal laboratory data will be presented.

Table 3: Criteria for Potentially Clinically Significant Laboratory Values

Test	Criterion value
Serum chemistry	
Alanine aminotransferase (ALT)	≥3x ULN
Aspartate aminotransferase (AST)	≥3x ULN
Alkaline phosphatase (ALP)	≥3x ULN
Gamma-glutamyl transpeptidase (GGT)	≥3x ULN
Lactate dehydrogenase (LDH)	≥3x ULN
Blood urea nitrogen (BUN)	≥10.71 mmol/L
Creatinine	≥177 μmol/L
Bilirubin (total)	≥34.2 μmol/L
Hematology	

Test	Criterion value
Hematocrit	Men <0.37 L/L
	Women <0.32 L/L
Hemoglobin	Men ≤115 g/L
	Women ≤95 g/L
WBC counts	≤3 x 10  /L ≥20 x 10  /L
Eosinophils	≥10%
Absolute neutrophil count (ANC)	≤1 x 10  /L
Platelet counts	≤75 x 10  /L ≥700 x 10  /L
Urinalysis	
Hemoglobin	≥2 unit increase from baseline
Glucose	≥2 unit increase from baseline
Ketones	≥2 unit increase from baseline
Total protein	≥2 unit increase from baseline

ULN=upper limit of normal range; WBC=white blood cell

